4.5 Patient stratification

Subjects will be stratified according to sidedness⁵ and (K)RAS/BRAF mutation status of the primary tumor (right-sided *versus* left-sided and (K)RAS/BRAF wild-type *versus* mutation) of two reasons. Firstly, patients in good performance status (ECOG 0–1) with (K)RAS/BRAF wild-type tumor (which frequently is left-sided) will commonly and according to national guidelines be offered an irinotecan-containing regimen with the addition of an EGFR inhibitor. A block-randomization within each study stratum will ensure that this therapeutic option does not compromise enrolment onto any of the other groups (*c.f.*, [Paragraph 10.1](#)). Secondly, stratification will enable outcome analysis (PFS) within each of the defined groups, among which the study treatment may show differential effects. Ideally, tumor MSS status should be determined to avoid inclusion of MSI cases; however, the current logistics of this analysis at hospitals commonly

precludes it from being undertaken swiftly enough before the commencement of active therapy. In order to meet this challenge, tumor MSS status will be determined as per current practice. It is expected that approximately 5% of enrolled patients will harbor non-MSS tumor [Cancer Genome Atlas Network, 2012; Goldstein *et al.*, 2014], and the statistical power analysis (*c.f.*, [Paragraph 10.2.1](#)) has been adjusted to enable removal of these few cases before data analysis.

⁵ **Sidedness** is defined as follows: *right-sided*, primary tumor in cecum, ascending colon, or transverse colon; *left-sided*, primary tumor in splenic flexure, descending or sigmoid colon, or rectum.

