## 2.2. Randomization

The patients will be block-randomized into treatment arms with ratio 1:1 following a computer-randomized allocation sequence. The blocks will be defined according to sidedness and (K)RAS/BRAF mutation status of the primary tumor (right-sided versus left-sided and (K)RAS/BRAF wild-type versus mutation). The allocation sequence will be generated by the web-based Viedoc system.

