## 2.3. Sample size

Calculation of sample size was performed for PFS – the primary end point – and based on PFS data from recent publications. A median PFS of 9 months was assumed for the standard-of-care (control arm) [Cartwright, 2012; Tveit et al., 2012; Cremolini et al., 2015]. Regarding the therapy concept of ICB, there is no PFS data published as yet for the setting of interest. In the study of patients with treatment-refractory metastatic CRC, median PFS was not reached in the cohort with mismatch repair-deficient disease at the time of reporting [Le et al., 2015]. In the study of previously untreated patients with advanced non-small cell lung cancer, which is a tumor entity with considerably poorer prognosis than advanced CRC, patients with PD-L1-positive tumors that were randomized to ICB showed median PFS of 10.3 months compared to 6.0 months for standard chemotherapy [Reck et al., 2016].

Extrapolating to the setting of interest, with a median PFS of 9 months for standard-of-care, a median PFS twice as long (18 months) was entered for the sequential therapy. Assuming the exponential distribution of survival functions, the median PFS estimates were converted to hazard ratio (HR) of 0.5. Allowing for 10% censoring rate of subjects, the required sample size was estimated to be 40 patients in each arm to be able to show that HR of 0.5, implying the risk of a PFS event in the experimental group is 50% lower than in the control group, is significantly different from 1 with the power of 80% at significance level of 5%, given that log-rank test will be used.

However, it was necessary with several adjustments of the above calculations to maintain sufficient power. First, the sample size was adjusted to enable removal of a maximum of 5% enrolled cases with non-MSS tumor before data analysis. Next, keeping in mind the condition of patients, it is not unlikely that some will be lost from the study before a valid PFS event has been reached. Also, a number of analyses stratified by primary tumor sidedness and (K)RAS/BRAF mutation status will be performed. Hence, to enable high enough power in the statistical analysis, the sample size was increased by an additional 20%. After

incorporating the adjustments, the final sample size was estimated to be 100 patients, 50 in each arm, with 1:1 randomization.

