#### 5.2. Analysis methods

*Main statistical analyses.* The main statistical analysis is planned after the last patient has fulfilled the pre-defined follow-up period. PFS will be calculated from the day of randomization to first recorded disease progression according to RECIST v1.1 or when applicable iRECIST, or death. Patients who have not had disease progression at the time of final analysis will be censored at the date last known to be alive and progression-free. The analyses will compare the treatment groups in total as well as groups stratified by primary tumor sidedness and (K)RAS/BRAF mutation status.

*Interim analyses.* Interim analyses will apply to data on safety, tolerability, possible detrimental effects, and curative outcomes, and will be based on purely clinical judgment by the External Data and Safety Monitoring Committee. These types of data will be reported as the number of events.

*Descriptive statistics.* Demographic and clinical characteristics will be presented as means and standard deviations, medians with minimum and maximum values, or frequencies and percentages, as appropriate. Further statistical analyses will be separated to primary analyses, including only comparison of primary end point between two treatment arms, and secondary analyses, including stratified analyses on primary and secondary end points as well as number of analyses on secondary end points.

*Primary analysis.* Median PFS time will be compared between study arms by drawing Kaplan-Meier survival curves and performing log-rank test. HR with the corresponding 95% CI and p-values will be estimated by Cox proportional hazards model.

*Secondary analyses.* Distribution of PFS times stratified by the primary tumor sidedness and (K)RAS/BRAF mutation status will be illustrated graphically by Kaplan-Meier curves and compared by log-rank test. To assess the hazard rates for disease progression within each strata, Cox proportional hazards model will be estimated and, if appropriate, adjusted for relevant covariates. The results will be presented as HR with the corresponding 95% CI and p-values.

Safety. The number of serious adverse events (SAE) will be summarized and presented by trial arm. In addition, information will be given on the number of SAE per participant, together with details on the causality, expectedness, and outcome of each SAE experienced. Summaries of suspected unexpected serious adverse reaction (SUSAR) events will also be presented by trial arm.

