Tolerability. Summaries by trial arm will be produced to show the proportion of participants experiencing each grade of CTCAE toxicities overall and during each treatment cycle. For more detailed summaries, this information will also be broken down into the different types of toxicities.

QoL. This will be summarized for each treatment arm at study enrolment, completion of the active therapy of the first treatment sequence (after 16 weeks), and disease progression, using the consensus modules EORTC QLQ-C30, EORTC QLQ-CIPN20, and EQ-5D-5L. The data will be illustrated graphically and presented as mean scores with 95% CI at separate time points. The differences in QoL between two treatment arms throughout the study period will be assessed by estimating a linear mixed model with fixed effects for time and treatment arm and the interaction between these two. Random effects for patients will be included. A significant interaction will quantify differences between the groups and serve as an omnibus test.

Safety and tolerability in the treatment arms will be compared by  $\chi^2$  or Fisher's exact test, as appropriate.

ORR is defined as the percentage of patients with a confirmed CR or PR. The proportion of participants achieving at least PR will be summarized with corresponding 95% CI for each treatment arm. The difference between the trial arms in the proportion of participants achieving at least PR will also be presented with corresponding 95% CI. The difference between participants achieving at least PR and remaining participants will be assessed using logistic regression adjusting for treatment group and stratification factors. Odds ratios with corresponding 95% CI and p-values will be presented for all variables incorporated in the model.

SSCRR is defined as the percentage of patients with a confirmed resection of metastatic disease with microscopically free margin (R0). Corresponding analyses as those to be performed for ORR will be applied for SSCRR.

DOR is defined as the time from the first documentation of CR/iCR or PR/iPR to disease progression. DOR Kaplan-Meier curves will be drawn and compared by log-rank test. The median DOR with corresponding 95% CI will be presented by treatment group. Stratified analyses will be performed as well. The Cox proportional hazards model, adjusting for the stratification factors, will also be used to compare DOR

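### The primary PFS test and hazard ratio leave out the two factors that stratify randomisation, and differential effects are to be judged by low-powered tests within strata without an interaction test.

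*SAP*

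**What the plan says.** **Randomisation.** SAP 2.2 and Protocol 10.2.1 allocate 1:1 in blocks: "The blocks will be defined according to sidedness and (K)RAS/BRAF mutation status of the primary tumor". That makes two factors at two levels, so four cells. Neither document gives the prevalence of any cell.

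**Primary analysis.** SAP 5.2 and Protocol 10.4.4: "Median PFS time will be compared between study arms by drawing Kaplan-Meier survival curves and performing log-rank test". The HR comes from a Cox model with no strata or covariates named. The descriptive-statistics paragraph (SAP 5.2, Protocol 10.4.3) limits the primary analyses to the two-arm comparison and puts stratified analyses in the secondary set. SAP 5.4 plans nothing further, so no stratified PFS result is specified even as a sensitivity analysis.

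**Secondary endpoints.** "The Cox proportional hazards model, adjusting for the stratification factors, will also be used to compare DOR", and OS is analysed the same way. The logistic models for ORR and SSCRR also adjust for the factors. The DOR and OS log-rank tests are plain.

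**PFS by stratum.** Protocol 4.5 explains that "stratification will enable outcome analysis (PFS) within each of the defined groups", because the treatment effect may differ among them. SAP 5.2 and Protocol 10.4.5 do this with Kaplan-Meier curves, log-rank tests and Cox models within strata, reporting HRs, 95% CIs and p-values. SAP 3.1 makes no multiplicity adjustment but promises to report every analysis performed.

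**Sample size.** SAP 2.3 and Protocol 10.1 mention removal of non-MSS cases, patients lost before a PFS event, and the stratified analyses, and continue: "Hence, to enable high enough power in the statistical analysis, the sample size was increased by an additional 20" per cent. No stratum size or stratum power is stated.

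**The concern.** There are two separate issues.

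First, allocation balanced on two factors makes the arms more alike than the unstratified log-rank variance assumes. If the factors predict PFS, the unstratified test is conservative, and the unadjusted HR lies nearer 1 than the HR within strata. Power on the endpoint that sized the trial is given up for no stated reason, while the SAP's models for four secondary endpoints use the same factors.

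Second, the question in Protocol 4.5 is whether the effect differs between groups. Separate p-values do not answer it, because one significant and one non-significant stratum may have the same HR. With low power in each stratum, a uniform benefit would often look like a subgroup effect. SAP 5.2 uses a treatment-by-time interaction for QoL, but plans no treatment-by-factor interaction for PFS.

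**Working it through.** **Inputs from SAP 2.3.** Medians of 9 and 18 months, so that "the median PFS estimates were converted to hazard ratio (HR) of 0.5". The target is that this HR "is significantly different from 1 with the power of 80% at significance level of 5%, given that log-rank test will be used". I take the test as two-sided. "Allowing for 10% censoring rate of subjects, the required sample size was estimated to be 40 patients in each arm". Up to 5% non-MSS removal leaves about 95 of 100 for analysis. Twelve months of accrual from 1 March 2018 and last patient completed on 1 September 2020 (SAP 2.1) imply 18 to 30 months of follow-up.

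**1. The plan's own figure.** Freedman events = (1.96 + 0.84)² × ((1 + 0.5)/(1 - 0.5))², which rounds up to 71. Then 71/0.9 = 78.9, or 40 per arm, as stated. Schoenfeld gives 66 events and 37 per arm. The inflation 80 × 1.05 × 1.20 = 100.8 agrees with the final 100.

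**2. Stratified versus unstratified log-rank.** Simulation of 5,000 trials per scenario: 95 patients, four equal cells, balanced allocation within cells, exponential PFS with a control median of 9 months at the average prognostic level, follow-up uniform over 18-30 months. Cell sizes and prognostic HRs are assumptions.

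| Prognostic HR per factor | Power at HR 0.5, unstratified | Power at HR 0.5, stratified | Type I error, unstratified | Type I error, stratified |
|---|---|---|---|---|
| 1.0 | 81% | 80% | 4.5% | 4.5% |
| 1.5 | 78% | 79% | 4.3% | 5.0% |
| 2.0 | 74% | 79% | 3.5% | 5.4% |
| 2.5 | 65% | 76% | 2.7% | 5.3% |

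Across repeat runs the change from stratifying was about -1 to -2 points at 1.0, +1 to +2 at 1.5 and +5 to +7 at 2.0. The gain at 2.0 persisted with unequal cells that included one of about 10%. With both factors at 2.0, the estimated treatment HR was 0.53 unstratified and 0.49 stratified.

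**3. Power within strata at HR 0.5.** With d events, power is Φ(√d × ln 2/2 - 1.96) by Schoenfeld and Φ(√d/3 - 1.96) by Freedman.

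- *Event rates.* The plan's 10% censoring gives 90%. The plan's medians over 18-30 months give 83.7% (control) and 60.0% (experimental), mean 71.8%.
- *Equal quarter, low end.* 95 × 0.718/4 = 17.1 events: 30% (Schoenfeld), 28% (Freedman).
- *Equal quarter, high end.* 100 × 0.9/4 = 22.5 events: 38% and 35%.
- *Half-sample (one factor at a time).* 34.1 events: 53% and 50%. 45 events: 64% and 61%.
- *Unequal cells (95-100 patients, 10% censoring).* A 10% cell has 16-18%; a 40% cell has 50-55%.
- *What the increase buys.* At 80 patients and 10% censoring a quarter has 18 events and 29-31% power; at 100 it has 35-38%.
- *What 80% in every stratum would need.* 4 × 66/0.9 to 4 × 71/0.9, with each stratum rounded up: 296 to 316 patients.

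**4. Reading four stratum p-values.** If the hazard is halved in all four cells and each test has power p, the chance of a mixture of significant and non-significant cells is 1 - p⁴ - (1 - p)⁴: 73% at p = 0.28 and 83% at p = 0.38. Under the null, four disjoint tests at 5% give 1 - 0.95⁴ = 18.5% for at least one false positive. Testing the two levels of each factor in turn gives overlapping tests and about 16%.

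**5. Power of an interaction test.** With about 34 events per level, the SE of the log ratio of HRs is √(4/34 + 4/34) = 0.485. For a two-fold ratio, Φ(0.693/0.485 - 1.96) is about 30%; for a 1.5-fold ratio, about 13%.

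**The case against.** **The primary analysis is valid as written.** This stands. A reader might infer that ignoring the stratification factors inflates type I error; the simulation shows the opposite. The issue is efficiency. Its size depends on a prognostic strength that the documents do not quantify, and stratifying loses a little if neither factor matters. The HR shift is partly a change of estimand, from marginal to within-stratum.

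**PFS is not the only endpoint analysed without the factors.** This stands in part. The DOR and OS log-rank tests and the ORR difference with its CI are also unadjusted. The inconsistency lies in the regression models: they adjust for DOR, OS, ORR and SSCRR but not for PFS.

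**The sample-size text does not claim powered strata.** This stands. A reader might infer that claim from the word that opens the final sentence, but the stratified analyses are one of several reasons and no stratum power is given. The increase also covers losses and should stay.

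**A single power figure for the strata would mislead.** This stands. A reader might settle on about 30%, but that needs equal quarters and timeline-based events. The plan's own 10% censoring gives 34-38% for 95-100 patients, and the wording also allows analysis by one factor at a time, with 50-64%. No reading reaches 80% in all strata.

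**Part of the remedy is already planned, and the rest has low power too.** The stratum analyses are classed as secondary, stratum HRs with CIs are to be reported, and the absence of multiplicity adjustment is disclosed. An interaction test has only about 30% power for a two-fold ratio. It does address the question in Protocol 4.5, which separate p-values do not, but a non-significant interaction must not be read as equal effects.

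**Conclusion.** The point holds in two parts.

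The primary PFS log-rank test and Cox model omit the randomisation factors without a stated reason. The cost is power, not validity: about 1 to 2 points if each factor has a prognostic HR of 1.5, and 5 to 7 if each has 2.0, against a loss of about 1 to 2 points from stratifying if neither is prognostic. These figures assume HR 0.5, about 95 patients, exponential PFS and equal cells.

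The within-stratum tests cannot show that effects differ, and they have about 28-38% power per equal quarter or 50-64% per half-sample, on assumed prevalences. The 20% increase changes this little. The documents do not support saying that the plan claims these tests are powered, or that the factors are used only for them, since they also enter the secondary-endpoint models. The change should be made, but the validity of the primary result does not depend on it.

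**What to change.** 1. **Primary analysis (SAP 5.2, Protocol 10.4.4).** Specify a log-rank test and a Cox model stratified by sidedness and (K)RAS/BRAF status, with the unstratified results as sensitivity.
2. **Differential effects (SAP 5.2, Protocol 10.4.5).** Replace the within-stratum log-rank tests by a treatment-by-factor interaction for each factor. Show stratum HRs with 95% CIs, labelled exploratory. State that the interaction test has low power (about 30% for a two-fold ratio of HRs).
3. **Sample size (SAP 2.3, Protocol 10.1).** Keep the 20% increase for losses, and add that it does not give adequate power within strata.

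The cost is wording, with no change to sample size or data collection, plus about 1 to 2 points of primary power if neither factor is prognostic. Both documents must change together, or they will disagree. Protocol 10.4.1 allows the statistical plan to be amended until the day of database lock; the choice should be fixed before anyone sees PFS by arm.

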Laboratory analyses ¹³	X	X ¹⁴	X ¹⁴	X ¹⁴	X ¹⁴	
Urine analysis ¹⁵	X	X ¹⁴	X ¹⁴	X ¹⁴	X ¹⁴	
Treatment administration						
FLOX						
Nivolumab						
Evaluation procedure(s)						
CT ¹⁷	X	X				
Correlative study procedures						
Whole blood sampling						
Plasma and serum sampling	X	X				
PBMC sampling ¹⁹	X	X				
Functional MR liver acquisition ^{19,20}						
Liver/peritoneal biopsy sampling ²¹						

- 1 Repeat after break period with disease progression, continue until progressive disease on ongoing therapy.
- 2 Until disease progression.
- 3 Analysis on primary or metastatic tumor.
- 4 Only at visit 2.
- 5 By completion of the active therapy of the first treatment sequence (after 16 weeks), *i.e.*, at first visit in first treatment break.
- 6 Until all study drug-related AE are resolved, have returned to baseline, or are deemed irreversible; reported for at least 100 days after last dose administration of IMP.
- 7 To be undertaken if clinically indicated from V1 onward, but mandatory at the 30 days safety follow-up visit.
- 8 May be omitted if full physical examination has been undertaken 14 days or less prior to the first dose of trial treatment.
- 9 For WOCBP.
- 10 Within 24 hours prior to the start of study drug.
- 11 Every 4 weeks.
- 12 Every 4 weeks; in the control arm, for 30 days after the last dose of study drug; in the experimental arm, for 160 days after the last dose of study drug.
- 13 Laboratory tests: Hb, HCT, WBC (including differential counting), platelets, liver factors (ALT, AST, ALP, LDH, GGT, total bilirubin, total albumin, INR), creatinine or urea, Na, K, Ca, Mg, phosphate, glucose, TSH, free T4, CEA, Ca19.9, Ca125.
- 14 Until all study drug-related abnormalities are resolved, have returned to baseline, or are deemed irreversible.
- 15 Dipstick.
- 16 FLOX in control treatment arm, nivolumab in experimental treatment arm.
- 17 In addition to computed tomography (CT) scan, MR scans or other radiologic evaluations will be performed if indicated.
- 18 Baseline CT scan must be taken within 28 days prior to the start of study drug.
- 19 Participation is optional for study centers.
- 20 Patient must not present contraindication to the procedure. Procedure must be done before a metastatic lesion in the liver/peritoneum is sampled.
- 21 Baseline sampling is mandatory; follow-up sampling is optional.

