7.7.4 Withdrawal or discontinuation

When a subject discontinues or withdraws prior to trial completion, all applicable activities scheduled for the final trial visit will be performed at the time of discontinuation. Any AE which are present at the time of discontinuation will be followed in accordance with the safety requirements outlined in [Chapter 8](#).

Subjects may withdraw consent at any time for any reason or be dropped from the trial at the discretion of Clinical Investigator should any untoward effect occur. In addition, a subject may be withdrawn by Clinical Investigator or Sponsor if enrolment into the trial is inappropriate, the trial plan is violated, or for administrative and/or other safety reasons. A subject must be discontinued from the trial for any of the following reasons:

- AE/SAE as specifically described.
- The subject withdraws consent.
- Confirmed disease progression; *c.f.*, [Paragraph 7.6](#).
- Any clinical AE, laboratory abnormality, or intercurrent illness which, in the opinion of Clinical Investigator, indicates that continued participation in the study is not in the best interest of the subject.
- Intercurrent illness that prevents further administration of treatment.
- Clinical Investigator's decision to withdraw the subject.
- The subject has a confirmed positive pregnancy test.
- Non-compliance with trial treatment or procedure requirements.
- The subject is lost to follow-up.
- Administrative reasons.

After the end of treatment, each subject will be followed for 30 days for AE monitoring. Subjects who discontinue for reasons other than PD/iCPD will have post-treatment follow-up for disease status until disease progression, starting a non-study cancer treatment, withdrawing consent, or becoming lost to follow-up. After documented disease progression, information on survival will be obtained until death, withdrawal of consent, or the end of the study, whichever occurs first.

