8.1.1 Non-serious adverse event(s)

The term AE is used to include both SAE and non-serious AE.

Non-serious AE are CTCAE grade ≤ 2 events or reactions listed in the the IB/SmPC of nivolumab. For FLOX, non-serious AE are CTCAE grade ≤ 2 events. Non-serious AE do *not* need to be *reported*. Also, AE or SAE that are definitely due to disease progression do *not* need to be *reported*; *c.f.*, Paragraph 8.3.

If an abnormal laboratory value or vital sign is associated with clinical signs and symptoms, the sign/symptom should be *reported as an AE* and the associated laboratory result/vital sign will be considered additional information to be collected on the relevant CRF.

The collection of non-serious AE information will begin at initiation of study drug and last until 100 days from the last dose of study drug (the 100-day injunction pertains to experimental arm patients only). Non-serious AE will be followed to resolution or stabilization, or *reported as SAE* if they become serious. Follow-up is also required for non-serious AE that cause interruption or discontinuation of study drug and for those present at the end of study treatment as appropriate. Identified non-serious AE will be *recorded* on a designated page of the CRF.

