8.2 SAE (serious adverse events) collection and reporting

For nivolumab, the IB represents the reference safety information to determine expectedness of SAE for expedited reporting. For the FLOX regimen, the SmPC of each of the drug components represents the reference safety information. Following the subject's written consent to participate in the study, all SAE (in both study arms), whether related or not related to study drug, must be collected, including those thought to be associated with protocol-specified procedures. All SAE must be collected that occur during the screening period and within 100 days of the last dose of nivolumab. If applicable, SAE must be collected that relate to any later protocol-specified procedure.

Clinical Investigator must report any SAE that occurs after these time periods and that is believed to be related to any IMP or protocol-specified procedure, pertaining to the full duration of the study (c.f., Paragraph 7.8), which is in accordance with European Commission guidelines.

An SAE report must be completed for any event where doubt exists regarding its seriousness.

If Clinical Investigator believes that an SAE is not related to study drug, but is potentially related to the conditions of the study (such as withdrawal of previous therapy or a complication of a study procedure), the relationship must be specified in the narrative section of the SAE report form.

SAE, whether related or not related to study drug, and pregnancies, must be reported to Sponsor (or designee) within 24 hours of awareness of the event. SAE will be recorded on the Suspect Adverse Reaction Report form by the Council for International Organizations of Medical Sciences (CIOMS), c.f. Appendix 10. Pregnancies will be recorded on a Pregnancy Surveillance Form.

If only limited information is initially available, follow-up reports are required. All SAE must be followed to resolution or stabilization.

If an ongoing SAE changes in its intensity or relationship to study drug or if new information becomes available, the SAE report must be updated and submitted within 24 hours to Sponsor (or designee) using the same procedure used for transmitting the initial SAE report.

Sponsor's representative for SAE notifications has the following address:

[contact]

and

Cell Phone: ([contact]

Sponsor will immediately forward SAE notifications (in experimental arm patients) to the following address:

[contact]

or

Facsimile Number: (+1) [contact]

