## Treatment duration

- Expected treatment duration per patient:
  - Experimental arm: 18 months (until failure of treatment strategy)
  - Control arm: 9 months (until failure of treatment strategy)

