### 5. Analysis

#### 5.1. End point definitions

*Primary end point:* PFS; radiologic assessment every 8 weeks, according to the Response Evaluation Criteria in Solid Tumors (RECIST) and the RECIST consensus guideline for assessment of response to immune-modulating therapies, iRECIST.

*Secondary end points:*

Safety: incidence of adverse events (AE), as reported according to Common Terminology Criteria for Adverse Events (CTCAE) version 4.0 recorded on ongoing basis.

Tolerability: AE grading, as assessed by CTCAE v4.0 recorded on ongoing basis.

ORR: the percentage of patients with a confirmed complete response (CR) or partial response (PR).

DOR: the time from the first documentation of a CR or PR to disease progression.

SSCRR: the percentage of patients with a confirmed resection of metastatic disease with microscopically free margin (R0).

OS: the time from randomization to death of any cause.

QoL: assessment undertaken at study enrolment, completion of the active therapy of the first treatment sequence (after 16 weeks), and disease progression, using the consensus modules EORTC QLQ-C30, EORTC QLQ-CIPN20, and EQ-5D-5L.

*Tertiary end point:* Cost estimate; evaluation of the healthcare costs (relating to the sequencing procedures and administered medication) and health effects (quality-adjusted life years), expressed as incremental cost-effectiveness ratio, of the sequential therapy relative to the control group as comparator.

*Exploratory end points:* Various analyses will be undertaken for exploratory end points listed in 1.2.

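### Safety is tested on crude proportions with no exposure adjustment, so longer treatment in the experimental arm could be read as excess harm

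*SAP*

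**What the plan says.** SAP 5.1 defines the end point as "Safety: incidence of adverse events (AE), as reported according to Common Terminology Criteria for Adverse Events (CTCAE) version 4.0", with no person-time denominator. SAP 5.2, like Protocol 10.4.5, then states: "Safety and tolerability in the treatment arms will be compared by" a chi-square or Fisher's exact test. Tolerability is also summarised as proportions per grade, overall and by treatment cycle, and serious events are counted per participant. SAP 5.4 plans no further analyses. SAP 2.1 lists safety and tolerability among the outcomes on which the experimental arm may show superiority.

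On expected treatment, SAP 2.1 gives "Experimental arm: 18 months (until failure of treatment strategy") and "Control arm: 9 months (until failure of treatment strategy").

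Four places in the protocol describe how long events are collected after treatment:
- Section 8.1.1, on non-serious events, gives 100 days and adds that "the 100-day injunction pertains to experimental arm patients only".
- Section 8.2, on serious events, sets collection "within 100 days of the last dose of nivolumab" and states no equivalent end of window for the control arm.
- Section 7.7.4 says: "After the end of treatment, each subject will be followed for 30 days for AE monitoring".
- Footnote 6 of the flow chart (Chapter 6) has events "reported for at least 100 days after last dose administration of IMP", with no restriction by arm.

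**The concern.** The proportion of patients with at least one event rises with time under observation. If the experimental treatment prolongs disease control, its patients stay on therapy and under event collection longer, and the crude proportion rises even when the event rate per month is the same in both arms. The planned test cannot separate a more toxic treatment from one that is given for longer. Because safety is a comparative objective, a treatment that works could be reported as less safe partly because it works. Protocol 4.6 also hopes that sequencing will dampen the side effects of FLOX, and a crude comparison over unequal time could hide such a benefit.

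**Working it through.** **The plan's own exposure figures.** Protocol 5.5 describes an average patient in each arm.
- Control: 16 + 8 + 16 = 40 weeks to failure of strategy, of which 32 are active. At one cycle per 2 weeks this is 16 cycles, all FLOX.
- Experimental: 3 × (16 + 8) + 8 = 80 weeks, of which 3 × 16 + 8 = 56 are active, or 28 cycles.
- FLOX in the experimental arm: 3 × 4 + 2 = 14 cycles, or 4 × 4 = 16 if the fourth sequence is completed, as the same section also says.

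The ratio is therefore 18/9 = 2 for time on strategy, 28/16 = 1.75 for active cycles, and 14–16 to 16 for FLOX.

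**Assumptions.** The documents give no adverse-event rates, so control incidence is assumed and varied. The true event rate per unit time is the same in both arms. The test is Fisher's, two-sided at 5%; SAP 3.1 gives the 5% but not the sidedness. I take 48 per arm, which is 50 less about 5% with non-MSS tumors. Rejection probabilities are exact, by summing over both binomial distributions.

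**Formulas.**
- Constant rate, fixed times with ratio k: p(exp) = 1 − (1 − p(ctrl))^k. With p(ctrl) = 0.30 and k = 2: 1 − 0.70² = 0.51.
- Exponentially distributed durations: p = h/(h + λ), with λ = ln 2/median. A rate giving 30% over a fixed 9 months is h = −ln(0.70)/9 = 0.0396 per month. Control: 0.0396/(0.0396 + 0.0770) = 0.34. Experimental: 0.0396/(0.0396 + 0.0385) = 0.51.
- Front-loaded events (Weibull, shape 0.5, an assumption): k is replaced by √2 = 1.41.

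| Scenario, equal underlying rate | Control vs experimental | Fisher rejects |
|---|---|---|
| No imbalance | 30% vs 30% | 3% |
| Fixed 9 vs 18 months | 30% vs 51% | 47% |
| Fixed 9 vs 18 months | 50% vs 75% | 64% |
| Active cycles, 16 vs 28 | 30% vs 46% | 30% |
| Active cycles, 16 vs 28 | 50% vs 70% | 44% |
| Exponential, medians 9 and 18 months | 34% vs 51% | 31% |
| Exponential, medians 9 and 18 months | 50% vs 67% | 30% |
| Front-loaded, 9 vs 18 months | 30% vs 40% | 11% |
| Front-loaded, 9 vs 18 months | 50% vs 63% | 18% |

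For fixed 9 vs 18 months, control incidences of 10%, 20% and 40% give 15%, 33% and 59%. Where exposure differs, nearly all rejections point to excess harm in the experimental arm.

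**Post-treatment window.** Suppose, for illustration only, 100 days in the experimental arm and 30 in the control arm, with 50 patients per arm. With 9 months (274 days) of treatment in both arms, the time ratio is 374/304 = 1.23. A 30% control incidence becomes 36%, and Fisher rejects in 6% (3–9% over control incidences of 10–70%). With 18 vs 9 months, the rejection rate is 43% with 30 days in both arms and 60% with 100 vs 30. Duration is the main driver. The window matters little alone, but would add to a difference in duration.

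**The case against.** **The distortion is conditional.** A reader might infer that equal toxicity will appear as harm. The documents do not support that. The 18-month figure is an extrapolation (SAP 2.3); if durations are similar, little distortion remains, and if events occur mainly early it is much smaller. This stands.

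**Exposure does not double by drug.** Cumulative FLOX is about equal, so toxicity that follows FLOX cycles need not show a spurious excess. The additional cycles are nivolumab, which control patients never receive, and events caused by it are a real difference between the arms. This stands for FLOX-specific toxicity. The planned comparison is not limited to such events, however, and the remainder can accrue over the longer period.

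**100 days against 30.** A reader might infer that these are the windows by arm. No passage says so. The 30-day statement covers every subject, footnote 6 gives 100 days without restriction, and the limit to the experimental arm is stated for non-serious events, which SAP 5.5 mostly does not record (grade 3–5, plus grade 2 immune-related hepatotoxicity). Serious events are collected in both arms, and related ones remain reportable afterwards. What stands is a conflict between passages.

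**Mitigation in the plan.** The per-cycle summaries allow comparison at matched cycles, but are descriptive. The SAP's provision for adjusting methods when assumptions fail would not clearly be triggered, since unequal exposure does not breach an assumption of Fisher's test.

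**Cumulative incidence is a legitimate question.** Patients do experience the whole strategy, so the crude proportion should be kept.

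**Conclusion.** The concern holds as a gap in the analysis plan. Safety and tolerability are compared on crude proportions, with no exposure-adjusted analysis, in a trial whose sponsor expects twice the time on strategy in the experimental arm. At 30% control incidence and equal rates, a false difference would be declared in roughly 11% to 47% of trials depending on how exposure and event timing are modelled, against 3% with no imbalance. These figures rest on assumed event rates, 48 patients per arm, a two-sided test, and the hoped-for prolongation of treatment actually occurring. They are not a forecast of what the trial will show. The post-treatment windows are a separate and smaller matter: four passages conflict and must be reconciled. The PFS analysis and its sample size are unaffected.

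**What to change.** 1. In SAP 5.2, add exposure-adjusted incidence by arm: first events and all events per patient-month (or time to first event), with rate ratios and 95% confidence intervals. Base the comparative safety conclusion on these together with the crude proportions.
2. Optionally add incidence in the first 16-week sequence as supportive. A reader might take this as equal exposure, but only the planned duration is equal: control patients receive 8 FLOX cycles, experimental patients 4 FLOX and 4 nivolumab. Later events are also omitted, so it should not replace the whole-study comparison.
3. Reconcile Protocol 7.7.4, 8.1.1, 8.2 and footnote 6 of the flow chart, so that the events compared between arms are counted over the same post-treatment window.

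**Cost.** Items 1 and 2 need SAP wording and some extra analysis. Event onset and end dates (Protocol 8.9) and infusion times (7.4) are already recorded, and Protocol 10.4.1 allows changes to the plan until database lock. Rate ratios assume a roughly constant event rate, which should be stated beside them. Item 3 may affect data collection: the first 3-month follow-up visit (±7 days) can fall before day 100, and patients who start new anti-cancer therapy move to survival follow-up (Protocol 7.3.5).
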